2.14.2 Analysis for Data Monitoring Committee (DMC)

Regular interim analyses on risk-benefit evaluation will be performed for the independent DMC by an independent team of statisticians and programmers who are not otherwise involved in the conduct of the study. The data review will be done by the DMC. The DMC will be independent of Novartis and the team involved in the study conduct.

2.14.3 Blinded data reviews

The purpose of the blinded data reviews is to ensure an adequate sample size and follow-up time to address the scientific objectives of the study without un-necessarily exposing patients by adapting design features such as sample size and follow-up duration as indicated by the accumulating data.

Blinded data reviews will be conducted in this study for:

- (1) Blinded sample size re-estimation: relapse (and disability) related assumptions (primary endpoint) will be re-assessed based on a review of blinded data to adjust sample size if indicated by the accumulating data. This review will occur prior to the completion of enrolment.
- (2) Declaration of EOS: data collected by the study on relapse rates and disability worsening events will be monitored. EOS will be declared only once when sufficient

information has been collected to address the study's primary and key secondary objectives.

Details of the statistical analysis plan with respect to blinded data reviews are provided in the [BSSR SAP](#).

3 Sample size calculation

Sample size requirements for this study are primarily driven by the disability-related key-secondary endpoints. **A total of 900 patients will be randomized to study drug in a 1:1 ratio (450 per treatment arm)**. A second study of identical design with the same sample size will be conducted in parallel. Both studies are independently powered to address the primary endpoint (ARR) and all key-secondary MRI endpoints.

Key-secondary outcomes related to disability will be analyzed in the combined populations of both trials, provided the primary null-hypothesis can be rejected in both studies. Other secondary efficacy endpoints, as well as safety will be analyzed by study.

The total sample size of this study can be increased from 900 patients per study to a maximum of 1250 patients per study based on a blinded sample size re-estimation if either the blinded relapse rate or the event rate of 3mCDW is substantially lower than expected.

All sample size calculations were done in EAST 6, version 6.3, Cytel Inc.

Primary endpoint:

- **ARR:** The total sample size of 900 randomized patients for this trial is sufficient to achieve $\geq 90\%$ power for the demonstration of superiority of ofatumumab over teriflunomide based on the primary endpoint (ARR).

Key-secondary endpoints:

The power mentioned for the key-secondary endpoints is conditional on the successful rejection of the null hypothesis for the primary endpoint (ARR), and the successful rejection of all key-secondary endpoints that are to be tested at a higher hierarchical level. Multiplicity adjustments and the testing procedure are defined in [Section 2.5.3](#).

- **3mCDW:** A total sample size of 1800 patients across two studies of identical design is sufficient to provide $\geq 90\%$ power and for the demonstration of superiority based on the 3mCDW.
- **6mCDW & 6mCDI:** A total sample size of 1800 patients across two studies of identical design is sufficient to provide $\geq 80\%$ power for an analysis of 6mCDW and 6mCDI.
- **MRI endpoints:** A total sample size of 900 randomized patients for this trial is sufficient to provide $\geq 80\%$ power for all MRI endpoints which are part of the testing procedure (Number of Gd-T1 lesions per scan, annualized rate of new or enlarging T2 lesions, annualized rate of BVL).
- **NfL:** A total sample size of 900 randomized patients for this trial is sufficient to provide a $\geq 90\%$ power for an analysis of the NfL concentration in serum.

3.1.1 Sample size for the primary endpoint (ARR)

A negative binomial distribution of relapses is assumed for the primary analysis; this is a common assumption in MS. The demonstration of a relative reduction of the ARR in patients treated with ofatumumab ($\lambda_{\text{ofa}}=0.168$) compared with those treated with teriflunomide ($\lambda_{\text{ter}}=0.28$) by 40% ($\lambda_{\text{ofa}} / \lambda_{\text{ter}} = 0.6$) with a **power of 90%** at a one-sided alpha-level of 0.025 in a study with 1.5 years follow-up and under the assumption of a dispersion parameter $\kappa=0.82$ requires a sample size of 322 completers per treatment arm (644 completers for the study). Allowing for 20% uninformative dropouts equally distributed across treatment arms, a total sample size of **805 randomized patients** is required for the study to demonstrate superiority of ofatumumab based on ARR. The same sample size, with the same assumptions would provide approximately 95% power for the demonstration of superiority of ofatumumab over teriflunomide at a one-sided alpha level of 0.000625 ($=0.025^2$) using the pooled data from two studies of identical design. The formula proposed by [Keene et al. 2007](#) was used for the sample size calculation for the primary endpoint.

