9.8.1 Sample size for the primary endpoint (ARR)

A negative binomial distribution of relapses is assumed for the primary analysis; this is a common assumption in MS. The demonstration of a relative reduction of the ARR in patients treated with ofatumumab ($\lambda_{\text{ofa}}=0.168$) compared with those treated with teriflunomide ($\lambda_{\text{ter}}=0.28$) by 40% ($\lambda_{\text{ofa}} / \lambda_{\text{ter}}=0.6$) with a **power of 90%** at a one-sided alpha-level of 0.025 in a study with 1.5 years follow-up and under the assumption of a dispersion parameter $\kappa=0.82$ requires a sample size of 322 completers per treatment arm (644 completers for the study). Allowing for 20% uninformative dropouts equally distributed across treatment arms, a total sample size of **805 randomized patients** is required for the study to demonstrate superiority of ofatumumab based on ARR. A sample size of 900 patients per trial (driven by the 3mCDW endpoint), under otherwise the same assumptions as before, would provide approximately 95% power for the demonstration of superiority of ofatumumab over teriflunomide at a one-sided alpha level of 0.000625 ($=0.025^2$) using the pooled data from 2 studies of identical design. The formula proposed by [Keene et al. 2007](#) was used for the sample size calculation for the primary endpoint.

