The dispersion parameter of $k=0.82$ is assumed based on the values observed for relapse data in the fingolimod phase III program. In the pivotal teriflunomide phase 3 program $290/1086=27\%$ of the patients discontinued over 104 weeks ([O'Connor et al. 2011](#)) in one trial, and $348/1196=30\%$ over 130 weeks in another one ([Confavreux et al. 2014](#)). In OPERA I and OPERA II discontinuation rates were lower. For the purpose of the primary analysis we conservatively assume that 20% of the randomized patients will not contribute to the primary analysis at all. This is a conservative assumption because patients who discontinue prematurely from the study can contribute with partial data (relapse counts, exposure) to the primary analysis. In this information-based design patients will be followed until the end of the trial (see EOS criteria), rather than to be observed for a fixed time period. Based on the 3mCDW endpoint it is anticipated that the majority of patients will be exposed for 1 to 2 years. For ease of calculation a fixed follow-up time of 1.5 years is assumed for the primary endpoint. Of note, the power for the primary endpoint will depend on the actual follow-up. For instance, if all other assumptions were kept fixed but patients were followed for only 1 year instead of 1.5 years, the power in each cohort would drop to approximately 78%. If, on the other hand, patients were followed up for 2 years, the power for the primary endpoint would increase to approximately 95%.

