3.1.2 Sample size the number of GdT1 lesions per scan

We assume a negative binomial distribution of the number of Gd-T1 lesions per scan. Assuming 0.26 Gd-T1 lesions per scan for teriflunomide and a 90% relative reduction with ofatumumab (i.e. 0.026 Gd-T1 lesions per scan for ofatumumab), and a dispersion parameter $\kappa_{Gd}=5.3$ (as observed in the combined FREEDOMS and FREEDOMS II studies for the same parameter, data on file), a total sample size of 210 patients with available MRI scans would be sufficient to provide **90% power** for the statistical test at a one-sided alpha 0.025. Allowing for 20% dropouts, a total sample size of **264 randomized patients** (132 per arm) is required for this endpoint.

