3.1.3 Sample size for the annualized rate of new or enlarging T2 lesions

We assume a negative binomial distribution of the number of T2 lesions. Assuming 2.1 new or enlarging T2 lesions over 1.5 years for teriflunomide (1.4 new or enlarging T2 lesions per year with a mean follow-up of 1.5 years) and an 80% relative reduction with ofatumumab (i.e. 0.42 T2 lesions over 1.5 years; 0.28 lesions per year for ofatumumab), an average follow-up of 1.5 years, and a dispersion parameter $\kappa_{Gd}=3.1$ (as observed in the combined fingolimod Phase 3 placebo-controlled trials, data on file) for the same parameter), a total sample size of 66 patients with available MRI scans would be sufficient to provide **90% power** for the statistical test at a one-sided alpha 0.025. Allowing for 20% dropouts, a total sample size of **84 randomized patients** (42 per arm) is required for this endpoint.

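### As worded, SAP 3.1.1 ties about 95% pooled ARR power to 805 patients per study, which gives 91.3%; SAP 3.1.3 states 66/84 patients for T2 lesions where its own inputs give 74/94

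*SAP*

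**What the plan says.** **ARR.** SAP 3.1.1 assumes annualized relapse rates of 0.168 and 0.28, dispersion 0.82 and 1.5 years of follow-up. It concludes that 90% power at one-sided 0.025 "requires a sample size of 322 completers per treatment arm (644 completers for the study"), which becomes 805 randomized after a 20% dropout allowance. The next sentence reads "The same sample size, with the same assumptions would provide approximately 95% power for the demonstration of superiority of ofatumumab over teriflunomide", at one-sided 0.000625, using the pooled data of both studies. Protocol 9.8.1 has the same derivation but opens the corresponding sentence differently: "A sample size of 900 patients per trial (driven by the 3mCDW endpoint), under otherwise the same assumptions as before". The opening of SAP section 3, which plans 900 patients per study, says "A second study of identical design with the same sample size will be conducted in parallel".

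**T2 lesions.** SAP 3.1.3 assumes 2.1 against 0.42 lesions over 1.5 years (1.4 and 0.28 per year), dispersion 3.1, 90% power and one-sided 0.025. It states that "a total sample size of 66 patients with available MRI scans would be sufficient to provide" 90% power, or 84 randomized (42 per arm) with 20% dropout. Protocol 9.8.6 has the same inputs but gives 74 evaluable and 94 randomized (47 per arm). The one difference in the stated inputs is that the SAP adds "an average follow-up of 1.5 years, and a dispersion parameter" after the counts have already been given over 1.5 years.

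The SAP Introduction declares the SAP consistent with protocol version 02. SAP section 4, which lists changes from the protocol, mentions neither difference in its visible text.

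**The concern.** In SAP 3.1.1 the only randomized total in the paragraph is 805, so the reference back to an unchanged sample size points to 805. A design with 90% power at one-sided 0.025 in one study need not have 95% power at 0.000625 when two such studies are pooled, and the protocol attaches the 95% to a larger size. For T2 lesions, two controlled documents report different results from identical inputs, so at least one is wrong.

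What is at stake is the reliability of the sample-size section. A reader of the SAP alone would take away too high a pooled power for 805 per study, and a T2 sample size that does not deliver its stated power.

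**Working it through.** **Formula.** Protocol Equation 1 (section 9.7.2.3, derived in Appendix 5) gives the variance of the log rate ratio as V/n, with n patients per arm and V = 1/(λ₁T) + 1/(λ₂T) + 2κ. Hence

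- n per arm = (z₁₋α + z_power)² × V / [ln(λ₁/λ₂)]²
- power = Φ(|ln(λ₁/λ₂)| / √(V/n) − z₁₋α)

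Dropout is applied as n/0.8 per arm, rounded up.

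**The formula reproduces the plan's other figures.**

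- ARR: V = 1/(0.168 × 1.5) + 1/(0.28 × 1.5) + 1.64 = 3.968 + 2.381 + 1.64 = 7.989. With (1.960 + 1.282)² = 10.507 and [ln 0.6]² = 0.2609, n = 321.7, so 322 per arm. Information is 322/7.989 = 40.30, and 644/0.8 = 805. All match.
- Follow-up variations in SAP 3.1.1.1: at 322 per arm, power is 78.3% for 1 year and 95.2% for 2 years. The SAP says that at 1 year "the power in each cohort would drop to approximately 78" percent, and that at 2 years it would be about 95%. Both match.
- Gd-enhancing lesions (0.026 against 0.26 per scan, dispersion 5.3): n = 104.9, so 105 per arm, in agreement with "a total sample size of 210 patients with available MRI scans would be sufficient to provide" 90% power in SAP 3.1.2. Then 105/0.8 = 131.25, so 132 per arm, or 264. Both documents agree.

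**Pooled ARR power at one-sided 0.000625 (z = 3.227).** Two studies with 322 completers per arm give 644 per arm pooled. Two studies of 900 with 20% dropout give 360 per arm each, or 720 per arm pooled.

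| Randomized per study | Completers per arm, pooled | Power |
|---|---|---|
| 805 | 644 | 91.3% |
| 900 | 720 | 94.8% |

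For 805: √(7.989/644) = 0.1114; 0.5108/0.1114 = 4.586; 4.586 − 3.227 = 1.359; Φ = 0.913. The type II error is 8.7%, against the 5% implied. Exactly 95% would need 726.8 completers per arm pooled, or 726.8/0.8 = 908.4, about 909 randomized per study.

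Variants tried for 805 do not reach 95% either. A pooled-null variance gives 92.5%, and ignoring dropout altogether gives 97.1%.

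**T2 lesions.** V = 1/0.42 + 1/2.1 + 6.2 = 2.381 + 0.476 + 6.2 = 9.057, and [ln 5]² = 2.590. Then n = 10.507 × 9.057 / 2.590 = 36.7, so 37 per arm, or 74 evaluable. With dropout, 37/0.8 = 46.25, so 47 per arm, or 94 randomized. These are the protocol's figures.

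| Evaluable per arm | Power |
|---|---|
| 33 (SAP, 66 in total) | 86.7% |
| 37 (Protocol, 74 in total) | 90.2% |
| 360 (900 less 20%) | >99.9% |

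**A likely source, by inference only.** If the 1.5-year counts are multiplied by 1.5 a second time, the means become 0.63 and 3.15, V = 1.587 + 0.317 + 6.2 = 8.105, and n = 32.9. That gives 33 per arm, or 66; 33/0.8 = 41.25, so 42 per arm, or 84. This is exactly the SAP's pair.

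**The case against.** The strongest counter-argument on ARR is that the sentence is ambiguous and nothing was miscalculated. SAP section 3 opens with 900 patients and speaks of a second study of equal size in that sense. Read that way, 94.8% is approximately 95%, and the two documents agree on 322, 644, 805 and the 95% itself. Only the size attached to the 95% is in doubt. This stands as a possible account of intent. It does not remove the need for an edit, because 900 is absent from SAP 3.1.1 and 805 is the nearest antecedent.

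On T2, the SAP says the calculations were done in EAST 6 and names a formula only for the primary endpoint, so the ARR formula is an assumption here. Other null variances give smaller numbers: about 34 per arm (68) with a pooled-null variance and about 32 per arm (64) with a control-rate null variance. Neither returns 66, and the pooled-null version gives about 68 per arm for Gd lesions where both documents imply 105. The formula used here reproduces the Gd figure and the protocol's T2 figure exactly.

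It is also fair to say that neither figure drives anything. The testing procedure in SAP 2.5.3 contains no pooled ARR test; there, 0.000625 is the error rate that follows from rejecting in both studies. The disability endpoints set the sample size, and the end of study is set by information and event counts. That limits the consequence but does not make the figures right.

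**Conclusion.** Both points hold. As worded, SAP 3.1.1 overstates pooled ARR power by 3.7 percentage points (95% against 91.3%). If 900 was meant, the power is right and the sentence points to the wrong sample size. SAP 3.1.3 is wrong on its own inputs: it is short by 8 evaluable and 10 randomized patients, and its 66 evaluable patients give 86.7% power, not 90%. The T2 conclusion rests on applying the plan's negative binomial formula to T2 counts, which the matches on ARR, Gd lesions and the protocol's own T2 figure support. The double use of 1.5 years is an inference about the cause, and the conclusion does not depend on it.

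These are errors of stated figures, worth correcting because the SAP declares itself consistent with the protocol. The design, the planned 900 per study, the tests and the alpha levels are unaffected.

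**What to change.** - **SAP 3.1.1:** attach the 95% explicitly to 900 patients per study, as Protocol 9.8.1 does. Alternatively, keep 805 and state about 91%.
- **SAP 3.1.3:** replace 66 evaluable and 84 randomized (42 per arm) with 74 and 94 (47 per arm), as in Protocol 9.8.6, and delete the repeated follow-up phrase.
- **Optional:** Protocol 9.8.4 and SAP 3.1.8 print the value of 1/0.614 as 0.163; it is 1.63, which agrees with the 63% increase in the same sentence.

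The two main corrections are text edits to the SAP only. If the SAP is closed, a correction note in the sample-size section of the study report does the same job. Nothing in the design or analysis has to change.

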3.1.1.1 Justification of assumptions for the primary endpoint

In the pivotal studies, patients treated with teriflunomide 14 mg (the control treatment for this study) had an ARR=0.32 ([Confavreux et al. 2014](#)) and ARR=0.37 ([O'Connor et al. 2011](#)). In an additional phase 3 study of teriflunomide versus Interferon beta-1a, patients treated with teriflunomide 14 mg had an ARR=0.26 which was not significantly different from that observed in patients treated with Interferon beta-1a (ARR=0.22). For the purpose of this study an ARR=0.28 is assumed for patients treated with teriflunomide 14 mg.

Ocrelizumab is an anti-CD20 monoclonal antibody with a similar mode of action as ofatumumab but is administered as infusion. In the ocrelizumab phase 3 trials an ARR of 0.156 (OPERA I) and 0.155 (OPERA II [Hauser et al. 2015](#)) were observed for patients treated with Ocrelizumab 600 mg, the corresponding interferon beta-1a controls had an ARR of 0.292 (OPERA I) and 0.290 (OPERA II); the corresponding relative reductions in ARR were 46% (OPERA I) and 47% (OPERA II). In the ocrelizumab phase 2 trial, patients treated with ocrelizumab 600 mg had an ARR=0.13, those treated with 1000 mg an ARR=0.17 ([Kappos et al. 2011](#)). Compared with the Interferon beta-1a control in the same trial (ARR=0.36), ocrelizumab 600 mg and 2000 mg reduced the ARR by 64% or 53%, respectively. Compared to placebo controls from the same trial (ARR=0.64), ocrelizumab 600 mg and 2000 mg reduced the ARR by 80% or 73%, respectively.

Ofatumumab 60 mg every 12 weeks administered subcutaneously showed in the phase 2 trial (unpublished data) approximately 34% relative reduction in relapse rate versus placebo over the first 24 weeks, but 60% in the second 12 weeks (week 12 to 24). The relative reduction of Gd-enhancing lesions of approximately 90% observed in patients treated with ofatumumab relative to those treated with placebo was similar to that observed with ocrelizumab and placebo, suggesting similarly strong anti-inflammatory potency of ofatumumab and ocrelizumab. Based on the combined findings, a relative reduction in the ARR of 40% is assumed between patients treated with ofatumumab compared to those treated with teriflunomide, which corresponds to an absolute ARR=0.168 for patients treated with ofatumumab, similar to that observed with ocrelizumab in phase 2 and 3.

The dispersion parameter of $k=0.82$ is assumed based on the values observed for relapse data in the fingolimod phase III program. In the pivotal teriflunomide phase 3 program $290/1086=27\%$ of the patients discontinued over 104 weeks ([O'Connor et al. 2011](#)) in one trial, and $348/1196=30\%$ over 130 weeks in another one ([Confavreux et al. 2014](#)). In OPERA I and OPERA II discontinuation rates were lower. For the purpose of the primary analysis we conservatively assume that 20% of the randomized patients will not contribute to the primary analysis at all. This is a conservative assumption because patients who discontinue prematurely from the study can contribute with partial data (relapse counts, exposure) to the primary analysis. In this information-based design patients will be followed until the end of the trial (see EOS criteria), rather than to be observed for a fixed time period. Based on the 3mCDW endpoint it is anticipated that the majority of patients will be exposed for 1 to 2 years. For ease of calculation a fixed follow-up time of 1.5 years is assumed for the primary endpoint. Of note, the power for the primary endpoint will depend on the actual follow-up. For instance, if all other assumptions were kept fixed but patients were followed for only 1 year instead of 1.5 years, the power in each cohort would drop to approximately 78%. If, on the other hand, patients were followed up for 2 years, the power for the primary endpoint would increase to approximately 95%.

3.1.2 Sample size the number of GdT1 lesions per scan

We assume a negative binomial distribution of the number of Gd-T1 lesions per scan. Assuming 0.26 Gd-T1 lesions per scan for teriflunomide and a 90% relative reduction with ofatumumab (i.e. 0.026 Gd-T1 lesions per scan for ofatumumab), and a dispersion parameter $\kappa_{Gd}=5.3$ (as observed in the combined FREEDOMS and FREEDOMS II studies for the same parameter, data on file), a total sample size of 210 patients with available MRI scans would be sufficient to provide **90% power** for the statistical test at a one-sided alpha 0.025. Allowing for 20% dropouts, a total sample size of **264 randomized patients** (132 per arm) is required for this endpoint.

3.1.3 Sample size for the annualized rate of new or enlarging T2 lesions

We assume a negative binomial distribution of the number of T2 lesions. Assuming 2.1 new or enlarging T2 lesions over 1.5 years for teriflunomide (1.4 new or enlarging T2 lesions per year with a mean follow-up of 1.5 years) and an 80% relative reduction with ofatumumab (i.e. 0.42 T2 lesions over 1.5 years; 0.28 lesions per year for ofatumumab), an average follow-up of 1.5 years, and a dispersion parameter $\kappa_{Gd}=3.1$ (as observed in the combined fingolimod Phase 3 placebo-controlled trials, data on file) for the same parameter), a total sample size of 66 patients with available MRI scans would be sufficient to provide **90% power** for the statistical test at a one-sided alpha 0.025. Allowing for 20% dropouts, a total sample size of **84 randomized patients** (42 per arm) is required for this endpoint.

3.1.4 Sample size for NfL

We assume a log-normal distribution for NfL concentrations. At month 3, geometric mean NfL concentrations of $\mu_1=25$ pg/ml in teriflunomide and $\mu_2=17$ pg/ml in ofatumumab treated patients are assumed, leading to an assumed treatment difference on the log-scale of 0.386 pg/ml. We further assume a common standard deviation of 0.700 pg/ml. A total sample size of 139 randomized patients with available NfL assessments would be sufficient to provide 90% power

for the statistical test at a one-sided alpha 0.025. Allowing for 20% dropouts, a total sample size of 174 patients (87 per arm) is required for this endpoint.

